To date, the predominant focus in physical activity research (including in cancer survivors) has been MVPA, since this intensity level has been found to confer the greatest health benefits.¹¹ However, older cancer survivors with physical functional impairment may have different needs, preferences, and barriers to being physically active, and thus require a different approach. Light-intensity activities ([LPA]; e.g., leisurely walking, gardening) are associated with better physical health,²⁷ including physical function^{28,29} and cardio-metabolic biomarkers,³⁰⁻³⁴ and better emotional well-being,^{27,35} independent of MVPA. Changing the focus from MVPA to LPA represents a more achievable and sustainable target for vulnerable populations such as older survivors with comorbidities. Despite emerging evidence of the health benefits of LPA, few rigorously designed RCTs have been conducted to evaluate the effects of LPA on physical and psychosocial health and well-being.

The majority of physical activity studies have been clinic- or center-based, focused on common cancers (breast, prostate, & colorectal), and targeted behavior.^{36,37} Few studies have focused on adults over 65 years or minority survivor populations (race-ethnic minorities, rural), and targeted outcomes meaningful to survivors (e.g., patient-reported outcomes).³⁶ Thus, there is a critical need for lifestyle activity interventions that are effective, low-cost, and accessible to older cancer survivors from diverse backgrounds, designed to be feasible, relevant, and meaningful for them. A home-based approach (both intervention delivery and outcomes assessment), expands the reach to underserved and underrepresented minority survivor populations.

We propose a home-based intervention focused on increasing light-intensity activity and reducing sedentary behavior throughout the day – more obtainable goals – for maintaining and improving physical function in vulnerable populations. By reducing barriers to participation, a home-based approach will expand the reach to underserved cancer survivors who are older or from rural areas.

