- Not currently participating in a program (personal, e.g., wearing an activity monitor, or structured, e.g., another study) to decrease sedentary time or increase physical activity.
- Not planning to move out of New Mexico within the next year.
- Own a smartphone, tablet or computer OR be willing to use a study provided smartphone capable of running the Fitbit app or website. Additionally, access to the internet or a Wi-Fi hotspot at least once per week is required. Smartphones and data plans will be provided to those individuals who are eligible but do not currently own a computer, tablet or smartphone. Participants loaned a study phone will be asked to sign form indicating they agree to return the phone at the end of the study.
- Availability of a family member or friend to be present (for safety) during remote assessment of physical performance tests.
- Willingness to be randomized to either study arm and to wear activity trackers (activPAL3 [sedentary behavior, standing, stepping] at weeks 1, 13, and 26 for 7 days; the Fitbit activity tracker during weeks 2-26 during waking hours if randomized to the immediate intervention arm; during weeks 14-26 if randomized to the delayed intervention arm).

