8.0 Study Endpoints

Primary endpoints include: a) process data (enrollment, retention and adherence rates; satisfaction with the program), and b) change in self-reported physical function.

Secondary endpoints include change in: a) subjective and objective measures of sedentary- and light-intensity activities, b) physical performance, and c) self-reported quality of life (QOL).

Safety endpoints:

All adverse events associated with the physical performance tests (see section 9.0) will be tracked. The performance tests incorporate movements typically undertaken during normal daily activities (standing from a chair, sitting on a chair), and thus represent tests that are more likely to be safely performed in the home. A friend or family member will be present during the remote assessment of physical performance, which is conducted in the study participants' homes. Safety checks will be made prior to the performance tests (see section 13.0 Potential Risks to Subjects / Protection Against Risks).

Additionally, study participants will be encouraged to report any “emergencies or events” by calling the toll-free study number. See Data Safety and Monitoring Plan for more details.

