Lifestyle Activity Intervention: The goal of the intervention is to be more active throughout the day, every day – a whole-of-day approach - without regard for frequency, intensity, or duration of activity bouts. To promote gradual and sustained change, participants will be asked to increase the number of steps per day (above their individual baseline level) during weeks 3-12, and then work to maintain their goals during weeks 13-25 (**Table 3**). The target of 3,000 extra steps per day represents approx. 30 extra minutes of LPA,⁴⁵ which is associated with health benefits.^{27,46} To encourage activity throughout the day (and reduce SB), participants will work towards 10 of 14 active hours per day (defined as >250 steps/hour in Fitbit). Frequent interruption of sitting is associated with better cardiometabolic health.^{21,47-49} In accordance with SDT and MI, participants will choose their own strategies for becoming more active and achieving their weekly goals with guidance and (technology) support from their health coach. A menu of ideas will be provided in their education materials, but participants will be encouraged to identify options that work best for their lifestyle.

Table 3. Intervention Schedule			
Week	# Active Hours/day	Steps/day (above baseline)	Minimum # days / week
1	Baseline assessment randomization, Fitbit mailed to participant		
2	Establish Fitbit baseline data		
3-4	6	1000	3,5
5-6	7	1500	3,5
8-8	8	2000	3,5
9-10	9	2500	3,5
11-12	10	3000	3,5
13	Post-intervention assessment		
14-25	Maintain goals (no study contact)		
26	3-months post-intervention assess.		

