Physical Activity and Sedentary Activity (secondary outcomes) Subjective Measures: (1) Godin leisure-time activity questionnaire will be used to screen for eligibility and to provide context for activities that changed in frequency, intensity, and duration during the intervention as objectively measured by activPAL. Godin's is a short survey with low respondent burden. ⁵³ (2) The PACE Adult Sedentary Behavior Questionnaire will be used to estimate self-reported sedentary activities during a typical weekday and during a typical weekend. Response items range from none to 6 or more hours per day for nine common activities (e.g., watching television, using a computer, reading, etc.) ⁵⁴ . Self-reported SB will provide context for SB measured objectively by ActivPAL3™ monitor. Note: Objective Measures: Daily LPA, MVPA, and SB will be objectively measured before and after the intervention using the activPAL3 monitor ⁵⁵ . The ActivPAL3, worn on the thigh, ⁴¹ includes both a triaxial accelerometer and an inclinometer (to detect change in posture, i.e., sitting vs. upright posture) and is the gold standard in SB research. ^{27,56-59} Operational definitions: ⁵⁶ (a) Total LPA & MVPA: sum of stepping bouts with a step rate of <100 and ≥100 steps per minute, respectively for activPAL. (b) Total SB: sum of all sitting/lying bouts. (c) Total steps per day. (d) Total waking hours with ≥250 steps. ^{60,61} Note: Fitbit™ and mobile app are used by study participants to monitor their (in)activity in real-time & prompt behavior change. The data (steps per day, hours/day with >250 steps) downloaded from the Fitbit website will only be used to assess adherence to the intervention; not to evaluate the secondary outcome.	X	X	X

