10.0 Data and Specimen Management

Data Management

Each participant will be assigned a unique number to identify their data. This unique number will be placed on each document (questionnaires) and included in each electronic file name (accelerometer data files created by software used to download the data) to identify the participant.

Data from questionnaires will be entered into a REDCap database. Only essential study personnel will have access to this database. Data entry will be tied to the unique number assigned to the study participant.

Data from the activPAL accelerometers will be downloaded using the PAL Technologies software packages and stored on a secure data server at UNM. The files will be identified by unique study ID number and assessment (baseline, post-intervention, or 3-month follow-up).

A data collection form will be used by the study personnel conducting the remote assessment of physical performance. This form will be identified using the unique study ID number. Data from this form will be entered into the REDCap database.

All paper files, including consent forms, will be stored in locked drawers. All electronic files, including audio recordings and video recordings will be stored on a secure data sever at UNM. All electronic files will be destroyed 3 years after the study closes. .

Recorded audio files with the Health Coaches will be saved on a secure server at UNM and saved with the unique Study ID number.

Recorded videos of remote physical performance tests will be saved on a secure server at UNM and saved with the unique study ID number.

Statistical Analyses

Overview: Outcome variables violating the normality assumption will be transformed prior to analyses. The pattern of missing data will be evaluated,⁷³ and the appropriate procedures for multiple imputation will be utilized. Primary analyses will be performed according to the intent-to-treat principal; as this is a feasibility study, per-protocol analyses also will be explored. ActivPAL3™ data will be downloaded using associated software, and analyzed using SAS and R software. Raw and event data (start/stop time for sitting/lying, standing, and stepping) will be processed using standard methods, e.g., determining valid wear time,⁷⁴⁻⁷⁶ threshold values for activity intensity,^{27,77,78} etc. Standard compliance criteria will be used (≥ 4 days with ≥ 10 hours/day).^{27,79} Quality controls (daily logs, visual examination of heat maps) will be used to check

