13.0 Potential Risks to Subjects / Protection Against Risks

This trial poses minimal risk, since the intervention specifies only light-intensity physical activity (e.g., standing, walking), which the participants are likely to already be doing, and thus may just be increasing in frequency or duration. Individuals for whom unsupervised light-intensity activity is not appropriate will be excluded from the study per the eligibility criteria. Nevertheless, there are some potential risks associated with the objective measure of sedentary activity. Sedentary activity will be assessed with a small, light-weight monitor (ActivPAL3™) worn on the thigh, and attached to the skin via an adhesive. If the attachment

PROTOCOL TITLE: Whole-of-Day Approach to Physical Activity in Older Cancer Survivors

causes any discomfort or irritation during the one week of data collection, the monitor will be moved to a different location if possible.

The remote assessment of physical performance poses minimal risk, since the two performance tests primarily incorporate movements typically undertaken during normal daily activities (standing from a chair, sitting on a chair), and thus represent tests that are more likely to be safely performed in a home setting. Note that both the 30 second Chair Stand test and the 4-stage balance test (see **Table 2**) have been routinely conducted in adult populations with mild to severe functional impairment such as cerebral palsy, COPD, knee osteo-arthritis, low back pain, multiple sclerosis, Parkinson's disease, renal transplant, rheumatoid arthritis, stroke, vestibular disorders, and frail elderly.^{83,84} Also, remote assessment (using videoconferencing) of these physical performance tests were determined to be safe, with no adverse events.⁸⁵⁻⁸⁷

A friend or family member is required to be present during the physical performance testing that is self-administered by the study participant in their own home. This friend or family member must be physically and mentally capable of providing support if needed, and have access to a telephone to request medical help, if needed. Additional protection against risks during the physical performance tests will include the following:

- A fall assessment will be administered prior to the tests. Frequent fallers will require 2 people to stand nearby the study participant during the tests to provide support if needed.

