14.0 Potential Benefits to Subjects

The current state of physical activity research is as follows: a) regular physical activity has numerous benefits; however, only a minority of older adults, including older cancer survivors, are physically active at the recommended levels, b) sedentary behavior, especially prolonged periods of uninterrupted sitting, has deleterious effects on health, even among individuals who exercise, and c) light-intensity activity is associated with better physical

PROTOCOL TITLE: Whole-of-Day Approach to Physical Activity in Older Cancer Survivors

health and psychosocial well-being. Since older cancer survivors spend up to 70% of waking hours in sedentary activities and seldom exercise, a potential benefit of participating in the proposed study is behavior change leading to increased light-intensity physical activity and reduced sedentary time. Additional potential benefits include improved physical function and quality of life. The proposed intervention is aimed at determining the feasibility and acceptability of a novel intervention to increase light-intensity activity throughout the day, ideally through at least minimal bouts of stepping each hour. If the intervention is feasible and acceptable to participants, and the data show promise, then this approach could be used to encourage inactive cancer survivors to adopt and maintain an active lifestyle, and may ultimately provide the impetus for further improvements in activity level through increased duration (longer bouts of continuous ambulation/activity) and/or intensity.

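### Does the activPAL light-intensity outcome need redefining because it counts stepping only, while the risk section names standing as light activity?

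*Combined protocol and SAP*

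**What the plan says.** Table 2 in Section 9.0 sets operational definitions for the activPAL monitor. The first reads "Total LPA & MVPA: sum of stepping bouts with a step rate of <100 and ≥100 steps per minute, respectively for activPAL". SB is the total of sitting and lying bouts. The other two are steps per day and waking hours with at least 250 steps. Standing time is in none of the four.

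The monitor does record standing. Section 3.2 lists what it measures as "activPAL3 [sedentary behavior, standing, stepping", and Statistical Analyses in Section 10.0 says "Raw and event data (start/stop time for sitting/lying, standing, and stepping) will be processed using standard methods".

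Elsewhere LPA is described by example. Section 2.0 has "Light-intensity activities ([LPA]; e.g., leisurely walking, gardening". Section 13.0, arguing that the trial carries little risk, says "the intervention specifies only light-intensity physical activity (e.g., standing, walking". Section 8.0 names as secondary endpoints changes in "subjective and objective measures of sedentary- and light-intensity activities", and Section 1.1.b wants effect sizes for them.

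**The concern.** Read together, Sections 9.0 and 13.0 use one term for two things. Section 13.0 treats standing as light activity, while Table 2 leaves it out of LPA and out of SB. A participant who stands instead of sitting has done something the protocol calls light activity, yet the LPA outcome stays where it was.

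If the content of the LPA outcome were really open, both its baseline level and its between-arm difference would depend on a choice made later, possibly after the data had been seen. The results are meant to inform a larger trial, so that trial could be planned on an LPA effect of uncertain meaning. A reader might also fear that the plan cannot show what replaced sitting, because SB alone does not distinguish standing from stepping.

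**Working it through.** **1. What each definition counts.**

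| Activity in waking wear time | SB | LPA | MVPA |
|---|---|---|---|
| Sitting or lying | yes | no | no |
| Standing | no | no | no |
| Stepping below 100 steps/min | no | yes | no |
| Stepping at 100 steps/min or more | no | no | yes |

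The table has one reading. Standing falls outside all three columns, and the omission is explicit.

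**2. Effect of moving X minutes a day from sitting to standing.** SB changes by −X. LPA changes by 0 under Table 2, and would change by +X if standing were included. For X = 15, 30 and 60 the gap between the two LPA measures is 15, 30 and 60 minutes. X is hypothetical; the documents give no expected change in standing.

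**3. Can the listed outcomes show what replaced sitting?** Stepping is either below 100 steps/min or not, so LPA and MVPA together cover all of it. With SB restricted to waking wear time, for each participant:

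wear time = SB + standing + LPA + MVPA

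change in standing = change in wear time − change in SB − change in LPA − change in MVPA

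- Sitting replaced by standing, equal wear time: 0 − (−30) − 0 − 0 = +30 minutes of standing.
- Sitting replaced by light stepping, equal wear time: 0 − (−30) − 30 − 0 = 0 minutes of standing.

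So SB, LPA and MVPA read together separate the two cases. Section 10.0 already plans to determine valid wear time and, for participants' sleep, Section 9.0 provides a log. The sum holds in raw minutes per participant, not on transformed scales, so any derivation belongs before transformation. Standing events are also processed directly and can simply be totalled.

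**4. Does stepping-only LPA fit the intervention?** Table 3 sets goals in steps above baseline and in active hours, and an active hour is defined by a 250-step count. The tracker's prompt in Section 9.0 is triggered by too few steps. The educational materials and Section 14.0 both describe breaking up sitting by a little stepping each hour. No goal is set in standing time, and standing earns no credit toward any goal.

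**5. How much time might be standing?** Section 14.0 says "older cancer survivors spend up to 70% of waking hours in sedentary activities". Assume a 14-hour waking day: (1 − 0.70) × 14 × 60 = 252 minutes not sedentary. Assume also 3,000 to 8,000 steps a day at 60 to 100 steps/min: stepping takes 3,000/100 = 30 to 8,000/60 = 133.3 minutes. That leaves 118.7 to 222 minutes, or 47% to 88% of 252, as standing. The waking day, step counts and cadences are assumptions, and 70% is the top of the stated range. The figure describes a level; it says nothing about a between-arm difference.

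**6. The step conversion.** Section 9.0 says "The target of 3,000 extra steps per day represents approx. 30 extra minutes of LPA". Taken literally, 3,000/30 = 100 steps/min, the first value on the MVPA side. The figure is marked approximate, and 3,000/31 = 96.8 steps/min is already below the cut, so this is rounding.

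**7. Sample size.** The calculation rests on physical function. A difference of 8.1 with SD 10 and 25 per arm gives power 0.801 by the exact two-sided t-test, and 25/0.80 = 31.25, so 32 per arm after attrition. LPA does not enter.

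**The case for a change.** The strongest case for a change is about pre-specification. Sections 9.0 and 13.0 do disagree on whether standing is light activity. Section 10.0 adds a little slack by referring to published intensity thresholds without restating the Table 2 cut-point. Standing may fill much of non-sedentary time, and the intervention aims to displace sitting, so what takes its place matters to the trial's rationale. Participants choose their own strategies, and some may stand more. Listing standing time now would cost one line and use data already collected; leaving it out means that whether to report it is decided later.

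Part of this stands. The wording does not match, standing is not a listed activPAL outcome, and a flat LPA result must not be read as meaning that nothing replaced sitting. What does not stand is that the outcome is open to either reading. An example in a paragraph about risk does not compete with an entry headed as an operational definition, and no other passage offers a rival outcome definition. Listing standing as a further outcome would add an estimate without altering any planned one. Moving standing into LPA would be a trade-off: it would capture sit-to-stand change, but mix in a behavior that no goal rewards, and possibly one that takes up more time than the stepping the intervention targets.

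**Conclusion.** No change is needed. The Section 13.0 example is loose wording, and leaving standing out of LPA is a fair choice for an intervention built on steps. Followed as written, the plan gives sound estimates for SB and for light-intensity stepping.

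The consequence is bounded: each minute moved from sitting to standing lowers SB by one minute and leaves LPA unchanged. It affects the interpretation of one secondary outcome, not the feasibility outcomes, physical function or the 32 per arm. An analyst can describe the LPA result as light stepping and summarise standing minutes beside it from events already in the files.

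This rests on two conditions: that the Table 2 definition is the one applied, and that SB is confined to waking wear time so that the components add up. The 47% to 88% illustration carries no weight in the conclusion, because its step counts, cadences and waking day are assumed.

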10.0 Data and Specimen Management

Data Management

Each participant will be assigned a unique number to identify their data. This unique number will be placed on each document (questionnaires) and included in each electronic file name (accelerometer data files created by software used to download the data) to identify the participant.

Data from questionnaires will be entered into a REDCap database. Only essential study personnel will have access to this database. Data entry will be tied to the unique number assigned to the study participant.

Data from the activPAL accelerometers will be downloaded using the PAL Technologies software packages and stored on a secure data server at UNM. The files will be identified by unique study ID number and assessment (baseline, post-intervention, or 3-month follow-up).

A data collection form will be used by the study personnel conducting the remote assessment of physical performance. This form will be identified using the unique study ID number. Data from this form will be entered into the REDCap database.

All paper files, including consent forms, will be stored in locked drawers. All electronic files, including audio recordings and video recordings will be stored on a secure data sever at UNM. All electronic files will be destroyed 3 years after the study closes. .

Recorded audio files with the Health Coaches will be saved on a secure server at UNM and saved with the unique Study ID number.

Recorded videos of remote physical performance tests will be saved on a secure server at UNM and saved with the unique study ID number.

Statistical Analyses

Overview: Outcome variables violating the normality assumption will be transformed prior to analyses. The pattern of missing data will be evaluated,⁷³ and the appropriate procedures for multiple imputation will be utilized. Primary analyses will be performed according to the intent-to-treat principal; as this is a feasibility study, per-protocol analyses also will be explored. ActivPAL3™ data will be downloaded using associated software, and analyzed using SAS and R software. Raw and event data (start/stop time for sitting/lying, standing, and stepping) will be processed using standard methods, e.g., determining valid wear time,⁷⁴⁻⁷⁶ threshold values for activity intensity,^{27,77,78} etc. Standard compliance criteria will be used (≥ 4 days with ≥ 10 hours/day).^{27,79} Quality controls (daily logs, visual examination of heat maps) will be used to check

PROTOCOL TITLE: Whole-of-Day Approach to Physical Activity in Older Cancer Survivors

classification of accelerometer data. Accelerometer methods will be published according to guidelines.⁸⁰⁻⁸²

Aim 1 - Feasibility & Acceptability: For this feasibility study, we hypothesize that we will meet the accrual target of 64 inactive, older cancer survivors within 18 months, retain 80% of the sample, and to achieve 80% adherence/fidelity to the intervention. No formal statistical analyses are needed for these hypotheses.

Aim 2 - Preliminary estimates of effect sizes: We hypothesize that physical function scores will improve in the intervention group compared to the control group. We will obtain means and precision estimates for between-arm differences in physical function scores at each time point. A linear mixed-effects model will be used with group, time, and group by time interaction, adjusted for ethnicity, rural/urban status, and baseline values as needed. The appropriate variance-covariance structure will be selected to account for the potential correlation among repeated measurements from the same participant. The primary test of interest is the group by time interaction, indicating whether there was a difference between groups in the primary outcome over time. Similar analyses will be conducted for secondary outcomes.

Aim 3 - Process evaluation: will be conducted via a mailed survey. Process data (**Table 2**) and other study related outcomes will be reviewed with the PAB to identify next steps and strategies to ensure the most appropriate design and methods for the future, larger RCT, with potential for broad dissemination and implementation.

PROTOCOL TITLE: Whole-of-Day Approach to Physical Activity in Older Cancer Survivors

Power / Sample Size Calculation

Using a 2-sided, 2-sample t-test, with a significance level of 0.05 and 25 people per arm, we will have 80% power to detect a mean difference of 8.1 in physical function scores (a large effect size) with a standard deviation of 10. To allow for 20% attrition, we plan to enroll and randomize 32 participants per arm. The results of the feasibility trial will inform the design (sample size, effect size) of a larger trial powered to examine efficacy

Maintaining Confidentiality

The following steps will be taken to secure the data and to maintain confidentiality:

- Study participants will be assigned a unique study ID.
- All data collected will be identified with the unique study ID.
- Identifying information (e.g., name, address, etc.) will be kept separate from the participant's study data.
- The PI will have access to the electronic “link” between identifying information and the study ID (Excel spreadsheet). The link (Excel File) will be password protected and kept on a secure computer server.
- Only trained study staff will have access to the data.
- Other data collected during the study will be stored on a password and firewall protected server and accessed via secured computers in the Cancer Research Facility. Any paper forms, including informed consent forms will be kept in a locked file cabinet of the study staff for up to three years.
- Study staff are required to have completed training for the responsible conduct of research.
- For participants receiving a study purchased smartphone for use during the study, upon return to study staff, all data from the phone will be deleted prior to sending to another participant for use during the study.
- If a smartphone is provided to a study participant to use with either their Fitbit or assessment of physical performance, prior to mailing the phone to study participants, any identifying information from previous participants' use will be deleted.
- The videoconference sessions (such as Zoom or Skype) will be recorded and the files will be stored on a secure computer server. The files will be password protected and the file name will not include any identifying information (e.g., study ID number rather than participant's name). These video files will be saved in a limited-access (only key personnel) folder on the secure server for up to 3 years upon completion of the intervention trial. This time will allow for publication of the study results and to allow the PI to retrieve any additional information to inform the remote assessment for the future definitive trial, if needed.

